**A Double-Blind, Placebo-Controlled Study of Dronabinol in Trichotillomania and Other
Body focused Repetitive Behaviors**

IRB: 18-0542
Version: 06 June 2020

[name], J.D., M.D., M.P.H.
University of Chicago
Chicago, IL

A Double-Blind, Placebo-Controlled Study of Dronabinol in Trichotillomania

This clinical trial will be conducted in the spirit of Good Clinical Practice (GCP) and in accordance with this IRB approved protocol. No deviation from the protocol will be implemented without the prior review and approval of the IRB except where it may be necessary to eliminate an immediate hazard to a research subject. In such a case, the deviation will be reported to the IRB as soon as possible.

Investigational Agent and Dosing

Dronabinol 5mg to 15mg po qday

Population

The population to be studied for this trial is 50 men and women ages 18-65 who have a current DSM-5 diagnosis of trichotillomania or other body focused repetitive behavior (BFRB) (e.g., skin picking disorder).

Project Goals

The goal of the proposed study is to evaluate the efficacy and safety of dronabinol in trichotillomania. 50 subjects with DSM-5 trichotillomania or other BFRB will receive 10 weeks of double-blind dronabinol or placebo. The hypothesis to be tested is that dronabinol will be effective and well tolerated in patients with trichotillomania or other BFRBs compared to placebo. The proposed study will provide needed data on the treatment of disabling disorders that currently lacks a clearly effective treatment.

Background

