50 individuals with trichotillomania or skin picking disorder will be recruited for a double-blind, placebo-controlled pilot study in which dronabinol or placebo is administered in a 1:1 fashion. All 50 subjects will have trichotillomania or skin picking disorder per DSM-5 criteria. Following baseline measures, all subjects will be randomized to either dronabinol or placebo and seen every 2 weeks for the first four weeks and every 3 weeks for the remainder of the 10-week period.

Participants will be started at 5mg po qday for 2 weeks, then 5mg po bid for 2 weeks and then 5mg TID for the remaining 6 weeks. Participants will only go up to the full dose if clinically needed. Efficacy and safety measures will be performed at each visit.

The study will be conducted in accordance with the International Conference on Harmonization Guideline for Good Clinical Practice, all local ethical and legal requirements, and the World Medical Assembly (Declaration of Helsinki). The study protocol and procedures will be approved by the University of Chicago's institutional review board prior to any recruitment. Written informed consent will be required for study participation.

Randomization of drug will be conducted in blocks of eight. The blind will be assessable to the study subject at all times by calling the pharmacy number listed on the medication bottle. The investigational pharmacy will follow proper accountability procedures in regards to both randomization of the study drug and holding of the blind.

Subjects:

Inclusion criteria:

- 1) men and women age 18-65;
- 2) current DSM-5 trichotillomania or skin picking disorder; and
- 3) Ability to understand and sign the consent form.

Exclusion criteria:

- 1) Unstable medical illness based on history or clinically significant abnormalities on baseline physical examination
- 2) Current pregnancy or lactation, or inadequate contraception in women of childbearing potential
- 3) Subjects considered an immediate suicide risk based on the Columbia Suicide Severity rating Scale (C-SSRS) (www.cssrs.columbia.edu/docs)
- 4) Past 12-month DSM-5 diagnosis of psychosis, major depressive disorder, bipolar disorder, mania, or a substance or alcohol use disorder
- 5) Illegal substance use based on urine toxicology screening
- 6) Stable dose of medications for at least the past 3 months
- 7) Previous treatment with dronabinol

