- Rapid Visual Processing Task (RVP)
- Spatial Working Memory Task (SWM)
- Cambridge Gambling Task (CGT)

Following-Up Visit Assessments

All follow-up visits will include all psychiatric measures (except the MINI which will be done at baseline only) and safety measures (adverse events, vital signs, C-SSRS). There will be four follow up visits for a total of five visits.

Subject Compensation

Subjects will be compensated \$20 per visit, for a total of \$100. Compensation will be given in the form of a check at the end of the study, as per University of Chicago protocol.

Safety Assessments

Safety and tolerability will be assessed using spontaneously reported adverse events data, Columbia–Suicide Severity Rating Scale (C-SSRS), vital signs, and by evaluating premature termination. Safety assessments (C-SSRS, sitting blood pressure, heart rate, adverse effects, and concomitant medications) will be documented at each visit. Subjects who are an immediate suicide risk will be removed from the study and appropriate clinical intervention (e.g. hospitalization) will be arranged. Urine pregnancy tests will be performed at the initial visit. Subjects who have a positive urine pregnancy test will be excluded from the study. Assessment of side effects will be done at each visit. AEs will be coded by system organ class (SOC) and preferred term (PT) using the Medical Dictionary for Regulatory Activities (Med- DRA) Version 11.1. The incidences of all AEs will be summarized descriptively. In terms of vital signs, those subjects with abnormal blood pressures will be assessed for symptoms of hypo- or hypertension. Asymptomatic subjects will be evaluated each visit for changes in vital signs. In the case of hypertensive emergencies (BP greater than 210/120), appropriate referral to the emergency room will be made. In the case of hypotension (BP less than 90/60), participants will be evaluated for symptoms of hypotension and if symptomatic, appropriate interventions will be made.

Seizure and seizure-like activity have been reported in patients receiving dronabinol. Therefore, history of seizures will be an exclusion criterion. If a seizure occurs, dronabinol will be discontinued. Participants will be advised to discontinue dronabinol and contact a healthcare provider immediately if they experience a seizure.

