- Any moderate adverse event which appears definitely, probably, or possibly related to study participation will be reported to the University of Chicago IRB in writing within 20 working days.
- Any mild adverse event will be summarized in the IRB annual progress reports.

Statistical Analysis

Design/Randomization

The study is a double-blind, placebo-controlled study. Participants will be randomized (1:1) to receive dronabinol or placebo by the University of Chicago Investigational pharmacy in block sizes of eight, using computer-generated randomization with no clinical information.

Due to the pandemic of COVID19, study participants can perform their baseline and follow-up visits online using encrypted Zoom instead of in person visits. All inventories will be assessed. Blood samples and urine toxicology, however, will be at the discretion of the study PI. In cases where they are considered medically necessary, the participant can have them drawn locally and submitted to the study team.

Efficacy Analysis

For statistical analysis, the full-analysis set will be defined as all participants who took at least 1 dose of the study drug and had at least 1 post-randomization primary efficacy assessment. The safety-analysis set will be defined as all randomized participants who took at least 1 dose of the study drug and completed at least 1 post-randomization safety assessment. Participants with trichotillomania and skin picking disorder will be grouped as one BFRB group.

We will compare the baseline characteristics of both groups using Fisher's exact test for categorical variables and the t test for continuous variables. We will calculate adherence to treatment, based on the number of pills returned at each visit, as the number of pills taken divided by the number of days in the study $\times 100\%$.

Primary endpoint analysis

The primary outcome measure will be the change from first randomization visit to study endpoint in total composite score on the NIMH Trichotillomania Symptom Severity Scale(s) and the Sheehan Disability Scale.

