The primary analysis of efficacy for continuous measures will be analysis of variance (ANOVA), with terms for treatment to assess differences between treatment groups in the change from first randomization visit to endpoint using the last observation carried forward. The primary analysis for global improvement and response categories will be the Cochran-Mantel-Haenszel test using the last observation carried forward. The primary analysis for $\geq 5\%$ reduction in weight will be Fisher's exact test using the last observation carried forward.

Secondary endpoints analyses

Secondary outcome measures will include the change from first randomization visit to study endpoint in CGI severity and improvement scales, self-reported hair pulling behavior using the MGH-HPS, self-reported skin picking behavior using the SP-SAS, the change in depressive and anxiety symptoms, change in quality of life, and impacts on personality markers. We will use a longitudinal analysis comparing the rate of change of the outcome during the treatment period between groups. The difference in rate of change will be estimated by random regression methods. The model for the mean of the outcome will include terms for treatment, time, and treatment-by-time interaction. To account for the correlation of observations within participants, we will use SAS procedure MIXED with a first-order antedependence covariance structure. The longitudinal analyses will use all available observations from all time points from all participants who completed a randomization visit evaluation.

Safety analyses

We will evaluate differences between groups in the incidence of treatment-emergent adverse events using Fisher's exact test. Descriptive statistics will be used to evaluate changes in laboratory values, blood pressure and heart rate.

Sample Size

The sample size was calculated for the co-primary endpoint of change from randomization. For 80% power to compare the change from randomization, assuming a true effect size of 0.5 between treatment group and the placebo group, 50 participants with a BFRB will be needed in each treatment group based on a 2-group t test at the .05 level of significance. Given the low rates of adverse events expected with dronabinol, we expect few drop-outs from the study and therefore a smaller sample is needed.

Data Management Plan

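### The tolerability hypothesis has no analysis that can support it: the only between-arm safety inference is a Fisher test for a difference, with about 25 per arm and no interval estimate

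*Combined protocol and SAP*

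**What the plan says.** Project Goals puts comparative tolerability inside the hypothesis to be tested: "dronabinol will be effective and well tolerated in patients with trichotillomania or other BFRBs compared to placebo". Primary Aim/Objective also names efficacy and safety together.

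For the analysis, Statistical Analysis, Safety analyses states: "We will evaluate differences between groups in the incidence of treatment-emergent adverse events using" Fisher's exact test. The same paragraph adds: "Descriptive statistics will be used to evaluate changes in laboratory values, blood pressure and heart rate". It gives no significance level, sidedness, confidence interval, margin or rule for interpreting a non-significant result.

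Safety Assessments describes the other material. It begins "Safety and tolerability will be assessed using spontaneously reported adverse events data" and goes on to list the C-SSRS, vital signs and premature termination. It also says "The incidences of all AEs will be summarized descriptively" and that side effects are assessed at every visit. The Monitoring Committee section provides for yearly independent review.

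On size, Methodology states "50 individuals with trichotillomania or skin picking disorder will be recruited for a double-blind, placebo-controlled pilot study", and Design/Randomization states "Participants will be randomized (1:1) to receive dronabinol or placebo". Sample Size is worked out for efficacy only.

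**The concern.** The hypothesis is that dronabinol does not carry an important excess of adverse events over placebo. A Fisher test addresses a different question, namely whether the data contradict equal incidence. Failing to reject equality is not evidence for it at any sample size, and is especially weak with about 25 per arm. The descriptive summaries, C-SSRS, vital signs and premature termination add information, but as planned none of them gives a between-arm estimate with its uncertainty.

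At stake is what the trial can say about tolerability. If the Fisher tests are non-significant, the stated analysis gives the reader no means of telling a small excess from one that is large but undetected.

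**Working it through.** **The plan's own figure.** There is no planning figure for safety. The only stated sample size is for efficacy: "50 participants with a BFRB will be needed in each treatment group", for 80% power at a standardised effect of 0.5. The normal approximation is n per arm = 2(z_α + z_β)²/d².
- One-sided 0.05: 2 × (1.645 + 0.842)²/0.25 = 49.5, so 50. This matches the plan.
- Two-sided 0.05: 2 × (1.960 + 0.842)²/0.25 = 62.8, so 63. This does not match.

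The figure says nothing about adverse events. It is also per group, whereas recruitment is 50 in total. I therefore use 25 per arm and show 50 per arm for comparison.

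**Inputs from Table 1.**
- Feeling high: 8–24% in the pooled data.
- Dizziness, sedation, nausea/vomiting, abdominal pain and paranoia: 3–10% in the pooled data.
- Any side effect in the earlier open-label trichotillomania study: 21.4%, 46.2%, 41.7% and 0% at the four dose steps, with 7 to 14 people per step.

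**Assumptions.** The documents give no placebo rates, so a range is used. Two-sided 0.05 and full retention are also assumed.

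**Method.** Power = Σ over a, b of Bin(a; n, p₁) × Bin(b; n, p₂) × 1[Fisher p(a, b) ≤ 0.05], where a and b are the numbers with the event on dronabinol and placebo.

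One case by hand: with no placebo events, the two-sided Fisher p for a events is 2 × C(25, a)/C(50, a).
- a = 5: 2 × 53,130/2,118,760 = 0.0502.
- a = 6: 2 × 177,100/15,890,700 = 0.022.

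At least 6 events are therefore needed. With a true rate of 24%, P(a ≥ 6) = 0.577; with 10% it is 0.033.

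| Event, dronabinol rate | Assumed placebo rate | Power, 25 per arm | Power, 50 per arm |
|---|---|---|---|
| High, 24% | 0% | 58% | 99% |
| High, 24% | 5% | 33% | 71% |
| High, 24% | 10% | 16% | 36% |
| Upper end of the 3–10% range, 10% | 0% | 3% | 38% |
| Upper end of the 3–10% range, 10% | 3% | 2% | 13% |
| Any side effect, 46.2% | 5% | 92% | >99% |
| Any side effect, 46.2% | 10% | 75% | 98% |
| Any side effect, 46.2% | 20% | 40% | 75% |

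At 25 per arm, 80% power needs a dronabinol rate of about 30%, 39%, 48% or 61% when the placebo rate is 0%, 5%, 10% or 20%. Those are excesses of roughly 30 to 41 points.

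**What an interval adds.** For 5/25 against 0/25, the Wilson 95% limits are 0.089 to 0.391 on dronabinol and 0 to 0.133 on placebo. The Newcombe limits for the difference of 0.200 are:
- lower: 0.200 − √[(0.200 − 0.089)² + (0.133 − 0)²] = 0.026;
- upper: 0.200 + √[(0.391 − 0.200)² + (0 − 0)²] = 0.391.

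So p = 0.0502 goes with an excess of +3 to +39 points. For 12/25 against 5/25, p = 0.07 and the interval is +2 to +50 points. For 6/25 against 2/25, p = 0.25 and the interval is −5 to +36 points. In the last case the test and the interval agree that zero is not excluded, but only the interval shows how large an excess remains possible.

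**The case against.** The strongest reply is that this is a self-described pilot, sized for efficacy, whose fuller hypothesis in the background section concerns only pulling or picking and psychosocial functioning. Low power for single adverse events is unavoidable at this size, and intervals will not establish tolerability either. Even identical counts leave wide limits: 0/25 against 0/25 has a Newcombe upper limit of 13 points, and 5/25 against 5/25 one of 22 points. This stands, and it is why the fix asks for a descriptive conclusion rather than a formal margin.

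Several stronger readings are tempting, but the documents do not support them.

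- **Tolerability is judged by Fisher tests alone.** It is not. Safety Assessments, the descriptive part of Safety analyses and the Monitoring Committee section all contribute. Fisher's test is only the sole between-arm inference.
- **Clear harms will come out non-significant.** This is too absolute. Excesses of about 30 to 41 points or more, depending on the placebo rate, have at least 80% power.
- **Safety Assessments and Safety analyses contradict each other.** Summarising all incidences does not rule out testing them as well, so the two are compatible.
- **Counts rest on spontaneous reports alone.** Safety Assessments also has side effects assessed at each visit. A scripted question would be a preference, not a correction.

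The 5 against 0 example sits right at the cut-off and sets a conservative exact test beside a Newcombe interval. It illustrates the point; the argument does not depend on it.

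**Conclusion.** The point holds in this limited form: the plan declares a comparative tolerability hypothesis and provides no between-arm analysis that could support it. For most adverse-event rates in Table 1, a non-significant Fisher result is likely even if a real excess exists. Power is 2–3% for events at 10% (placebo 0–3%) and 16–58% for feeling high at 24% (placebo 0–10%). For any side effect it depends heavily on the placebo rate, from 92% at 5% to 40% at 20%.

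A reader might infer that the investigators will treat p > 0.05 as proof of tolerability. No section says so; the plan simply leaves the interpretation open.

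The figures rest on assumed placebo rates, an assumed two-sided 0.05 and 25 evaluable per arm. Table 1's trichotillomania rates are open-label and by dose step, not ten-week incidences, so they indicate scale only. The logical gap, that a difference test cannot confirm absence of an important excess, depends on none of these. This is an inexpensive improvement that should be made; it does not threaten the efficacy analysis.

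**What to change.** In Statistical Analysis, Safety analyses:

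1. Make the main between-arm safety analysis the risk difference, dronabinol minus placebo, with a 95% confidence interval (for example Newcombe), in the safety-analysis set. Report it for any adverse event, each adverse-event term in Table 1, and premature termination.
2. Keep the Fisher p-values as supportive.
3. State that p > 0.05 is not evidence of tolerability, and that the tolerability conclusion is descriptive and reported with the upper confidence limit.

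The cost is a few sentences of SAP text and one table, with no extra participants, visits or data. The downside is that the tolerability statement becomes visibly less certain: at this size the upper limits will be wide even when the arms look alike.

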Given the serious personal consequences associated with trichotillomania and skin picking disorder, and the likelihood of success of dronabinol in treating both disorders, the aim of the present study was to examine the efficacy and safety of dronabinol vs placebo in adults with trichotillomania or skin picking disorder using a double-blind, placebo-controlled design.

We hypothesize that dronabinol will be more effective than placebo in reducing the frequency of hair pulling and skin picking and in improving overall psychosocial functioning after 10 weeks of treatment when compared to baseline.

Primary Aim/Objective

The aim of the present study is to examine the efficacy and safety of dronabinol vs placebo in adults with trichotillomania and skin picking disorder.

Co-Primary Endpoint(s):

The co-primary efficacy measures will be the change in hair pulling or skin picking frequency and urges to pull hair or pick skin for the past week as indicated by change in total score on the *NIMH Trichotillomania Symptom Severity Scale* (for TTM) or *Skin Picking Symptom Assessment Scale* (for SPD), reliable and valid clinician-administered measures (18-19), as well as the same scale modified for skin picking disorder, and the change in psychosocial functioning over the same time period using the *Sheehan Disability Scale* (20). The co-primary efficacy end points will be the change in these measures from baseline to week 10.

Secondary Aim/Objective

A secondary aim of the study is to examine the effects of dronabinol vs placebo on self-report measures of hair pulling, skin picking, quality of life, and measures of mood and anxiety.

Secondary Endpoint(s):

Secondary efficacy measures include the change in number of days per week pulling, the *Clinical Global Impressions–Improvement Scale* (CGI-I) rated global improvement of symptoms over time (results will be dichotomized as improved [CGI-I ratings of 1 or 2 very much/much improved] or not improved [CGI-I ratings of 3-7]) (20), the self-report *Massachusetts General Hospital Hairpulling Scale* (22), the *Skin Picking Symptom Assessment Scale*, the *Quality of Life Inventory* (23), the *Hamilton Depression Rating Scale* (24), the *Hamilton Anxiety Rating Scale* (25), and the *Tridimensional Personality Questionnaire*

Methodology

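### The plan says it needs 50 participants per group for 80% power but enrols 50 in total; about 25 per group gives 41% power on the planned test, and few drop-outs cannot close the gap

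*Combined protocol and SAP*

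**What the plan says.** The Sample Size section (Statistical Analysis) assumes an effect size of 0.5 and 80% power, and concludes that "50 participants with a BFRB will be needed in each treatment group based on a 2-group t test at the .05 level of significance". It adds that "we expect few drop-outs from the study and therefore a smaller sample is needed", without giving a drop-out rate, the smaller number, or its power.

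The enrolment figure is stated elsewhere. Methodology says "50 individuals with trichotillomania or skin picking disorder will be recruited for a double-blind, placebo-controlled pilot study", and Population and Project Goals also give 50 in total. Design/Randomization says "Participants will be randomized (1:1) to receive dronabinol or placebo".

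On the analysis, the Primary endpoint analysis section says "The primary analysis of efficacy for continuous measures will be analysis of variance (ANOVA), with terms for treatment". The Sample Size section refers to one endpoint ("The sample size was calculated for the co-primary endpoint of change from randomization"). The Co-Primary Endpoint(s) section names two measures, a symptom severity scale and the Sheehan Disability Scale, and says "The co-primary efficacy end points will be the change in these measures from baseline to week 10".

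**The concern.** The only power figure in the plan belongs to a trial twice the size of the one being run, and the reason given for the smaller size is not a valid one. An ethics board or monitoring committee reading the Sample Size section could believe that the trial has an 80% chance of detecting an effect of 0.5. The protocol also states an efficacy hypothesis ("We hypothesize that dronabinol will be more effective than placebo"), so its result will be read as a test of efficacy. If power is really near 40%, a null result could be mistaken for evidence that the drug does not work.

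**Working it through.** **Inputs**

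- Effect size d = 0.5, power 80%, level .05, two-group t test, 50 per group (Sample Size). Neither sidedness nor a drop-out rate is given.
- 50 participants in total (Population, Project Goals, Methodology).
- 1:1 allocation in blocks of eight (Methodology, Design/Randomization). Six full blocks give 24 + 24. The last two participants make it 25/25 or 24/26.
- ANOVA with a treatment term (Primary endpoint analysis). With two groups F = t², so the test rejects in either direction and equals the two-sided t test. Two-sidedness is therefore inferred from the analysis; it is not stated.

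**1. Reproducing the stated 50 per group**

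Normal approximation: n per group = 2(z_α + z_power)²/d².

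- One-sided .05: 2(1.645 + 0.842)²/0.25 = 49.5, so 50. The exact t calculation gives 50.15, and power at 50 per group is 79.9%.
- Two-sided .05: 2(1.960 + 0.842)²/0.25 = 62.8, so 63. The exact t calculation gives 63.77, so 64 (63 per group gives 79.5%).

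The stated 50 is thus an uninflated one-sided figure. It does not match the planned ANOVA.

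**2. Power at the sizes in question**

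Noncentral t with δ = d√(n/2) and 2n − 2 degrees of freedom. For n = 25, δ = 0.5 × √12.5 = 1.77. For n = 50, δ = 0.5 × √25 = 2.5.

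| Per group | Two-sided .05 | One-sided .05 |
|---|---|---|
| 25 (enrolled) | 41.0% | 53.9% |
| 50 (stated) | 69.7% | 79.9% |
| 64 | 80% | 88% |

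The noncentral F calculation gives the same two-sided results at 25 and 50 per group. A 24/26 split also gives 41.0%. The effect detectable with 80% power at 25 per group is 0.81 two-sided or 0.71 one-sided. At 50 per group it is 0.57 two-sided.

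**3. Precision at 25 per group**

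Expected 95% CI half-width = t(.975, 48) × √(2/25) = 2.011 × 0.283 = 0.57 SD, which is wider than the assumed effect itself.

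**4. The drop-out argument**

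Number to enrol = number evaluable/(1 − r), where r is the drop-out rate. Setting r = 0 leaves the number to enrol equal to the number evaluable, which is still 50 per group on the plan's own figure. For 100 to shrink to 50 by removing an allowance, the allowance would have to be 1 − 50/100 = 50%, and 25 evaluable per group would have to give 80% power. Step 2 shows that it does not.

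**5. Two co-primary measures**

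The 41% is for one measure alone. The documents give neither the correlation between the measures nor a success rule, so the following is illustrative. It assumes d = 0.5 on both measures and 25 per group, with 200,000 simulated trials per correlation.

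| Correlation | Both significant | Either significant, unadjusted |
|---|---|---|
| 0 | 17% | 65% |
| 0.5 | 25% | 57% |
| 0.9 | 34% | 48% |

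**The case against.** The plan never says that its test is two-sided, its hypothesis is directional, and its 50 per group comes out of a one-sided calculation. On that basis power at the enrolled size is 54%, and the statement that an effect of 0.5 would be missed more often than found no longer holds. Setting the plan's 80% against 41% also mixes two bases. Like for like, halving the sample takes power from 80% to 54% one-sided, or from 70% to 41% two-sided. This is fair as a matter of presentation, and the two-sided basis should be labelled as following from the ANOVA. It does not rescue the plan, since both bases fall well short of 80%.

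The Primary endpoint analysis section also speaks of a total composite score, so the two measures might be read as a single outcome. The 41% applies to any single continuous outcome with an effect of 0.5, a composite included.

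Finally, the study is called a pilot, and the section openly says that a smaller sample is used rather than claiming 80% power for 50. A pilot may be small, and nothing here requires more participants. But the label does not make a calculation for 100 apply to 50, and no power or precision is given for the trial as it will be run.

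**Conclusion.** The concern holds. The Sample Size section asks for 100 participants while the protocol enrols 50, and the drop-out argument does not connect the two. With all 50 analysed and a true effect of 0.5, power for each co-primary measure is 41% on the two-sided test implied by the ANOVA, so such an effect would be missed 59% of the time. Any loss from the analysis lowers the power further. Separately, 50 per group would itself fall short on that test, at 70%.

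The results rest on the plan's own effect size and level, on about 25 analysed per group, and on two-sidedness as inferred. The joint figures for two measures rest on further assumptions and serve only to show why the power must be stated per measure. The shortfall neither biases the estimate nor inflates type I error. It affects what the trial can show and how a null result may be read. The section must be corrected, because its only stated justification for the sample size does not apply to this trial.

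**What to change.** Delete the sentence that links few drop-outs to a smaller sample. Replace the statement of 80% power with 50 per group by text such as:

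> The test is two-sided at .05, as in the planned ANOVA. Fifty participants (25 per group), if all are analysed, give 41% power for an effect size of 0.5, and 80% power for 0.81, for each co-primary measure taken alone. The expected 95% CI half-width is about 0.57 SD. This is a pilot, and non-significance will not be read as absence of effect.

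The opening sentence of the section, which says that the size was calculated for the co-primary endpoint, should be reworded to agree.

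This costs wording only: no extra participants and no change to the planned ANOVA, although it makes the two-sided level explicit. The stated power becomes less favourable. If the sponsor wants to keep 80% power for an effect of 0.5 on the two-sided test, the alternative is 64 analysed per group (2 × 64 = 128 in total) for each measure alone, which would be a different and much larger trial.
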